### **3.9 Subgroup Analyses**

No subgroup analyses are prespecified in the protocol.

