4 STUDY DESIGN

4.1 Overall Design

This is a randomized, double-blind, placebo-controlled, parallel-group, multicenter study of oral MK-8527 administered QM in adults who are at low-risk of HIV-1 infection.

Approximately 350 participants will be randomized in a 2:2:2:1 ratio to 1 of 4 intervention groups: Group 1: MK-8527 (3 mg); Group 2: MK-8527 (6 mg); Group 3: MK-8527 (12 mg); and Group 4: Placebo. The screening window is 45 days and participants are allowed to rescreen 1 time (Section 8.11.1.2). The study population composition targets are: $\geq 30\%$ women, $\geq 30\%$ men, $\geq 80\%$ aged ≤ 35 years, and $\geq 30\%$ enrolled in Africa. Randomization will be stratified by sex (female, male) and region (Africa, non-Africa).

Participants will receive a total of 6 oral doses of the assigned blinded study intervention, 1 dose every 4 weeks, starting on Day 1. The final dose will be administered at the Week 20 visit. After the last dose, all participants will complete an 8-week blinded follow-up period.

The primary safety assessment will include all accumulated safety data during the intervention and follow-up period. AEs leading to discontinuation from study intervention will be assessed until Week 20 (last dose received). The Sponsor will perform an ongoing comprehensive review of safety parameters to assess for overall trends and outliers in reported AEs and event toxicities per standard monitoring procedures.

All participants will be evaluated for plasma MK-8527 PK drug levels, and a subset (approximately N=20 participants per intervention group) will be evaluated for MK-8527-TP in PBMC (PBMC Subset).

All participants and the investigators/clinical site personnel directly associated with study conduct will remain blinded to study intervention assignment through the 8-week follow-up period. The siDMC (internal) will be responsible for an interim safety review once 50% of the planned enrollment has reached Week 12 or discontinued from study intervention. Additional meetings of the siDMC may be triggered based on criteria outlined in the SAP/siDMC charter. An unblinded Sponsor team will review PK and safety data on an ongoing basis for the duration of the study. As per amendment 02, all Sponsor personnel except for a blinded medical monitoring team will be unblinded after the last expected Follow-up Week 4 visit, to enable earlier program strategic decision-making by the Sponsor.

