4.2.3 Rationale for Collecting Race and Ethnicity

The differential effect on efficacy and safety based on any demographic parameter, including race or ethnicity, cannot be predicted when evaluating a new investigational drug. Therefore, it is important to collect race and ethnicity data to ensure that there is not a differential effect based on these parameters and to gain assurance the results observed in the clinical study will be representative of the drug's use in a broader population. As an example, non-Caucasian patients were found to have higher plasma concentrations of EFV (an NNRTI) than their Caucasian counterparts, indicating an increased risk of EFV-induced toxicity in non-Caucasian people [Burger, D., et al 2005]. As another example, among people living with HIV in the United States, those of African heritage have been found to be less likely to maintain virologic suppression compared with other groups, and the factors contributing to this remain to be elucidated [Weintrob, A. C., et al 2009] [Ribaudo, H. J., et al 2013].

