4.2.4 Rationale for Collecting Gender Identity Data

Transgender people, defined as those whose gender identities and/or expressions differ from the sex assigned to them at birth, have a high prevalence and incidence of HIV infection globally [Poteat, T., et al 2016]. When considering HIV treatment, the WHO considers transgender people to be a separate key population because of their specific health needs and high vulnerability [Department of HIV/AIDS 2015]. Data will be collected in this study to assess clinical safety and toxicity in the transgender population.

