6.3 Measures to Minimize Bias: Randomization and Blinding

6.3.1 Intervention Assignment

Intervention randomization will occur centrally using an IRT system. There are 4 study intervention arms. Participants will be assigned randomly in a 2:2:2:1 ratio to MK-8527 (3 mg), MK-8527 (6 mg), MK-8527 (12 mg), or placebo, respectively.

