6.3.2 Stratification

Intervention randomization will be stratified according to the following factors:

1. Sex (female, male) (as assigned at birth)
2. Region (Africa, non-Africa)

The effects of study interventions may differ between these subgroups of sex and region. Therefore, sex and region are selected as the stratification factors to ensure that intervention groups will be well-balanced, and the effects of study interventions will not be confounded by those demographic characteristics.

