#### 3.8.1 Sample Size and Power for Safety Analyses

**Table 2** summarizes the power under various assumptions of the underlying standard deviation to detect the difference in the mean percent change from baseline in lymphocytes. The power is based on the two-sample t-test assuming 100 participants in the MK-8527 group and 50 in the placebo group. For example, if the standard deviation of percent change from baseline in both groups is 20, this study has 81.8% power to detect a difference at least as large as 10%.

Table 2 Power (%) to Rule Out Difference in Mean Percent Change from Baseline  
(With 100 Participants Randomized to MK-8527 and 50 Randomized to Placebo)

Underlying Standard Deviation of Percent Change from Baseline a	Underlying Difference of Mean Percent Change from Baseline in Lymphocytes (MK-8527 - Placebo)					
	-5%	-10%	-15%	-20%	-25%	-30%
10	81.8	>99.9	>99.9	>99.9	>99.9	>99.9
15	48.1	96.9	>99.9	>99.9	>99.9	>99.9
20	29.9	81.8	99.0	>99.9	>99.9	>99.9
25	20.8	63.1	93.1	99.6	>99.9	>99.9
30	15.8	48.1	81.8	96.9	99.8	>99.9

**Table 3** summarizes the differences in the incidence of AEs (MK-8527 minus placebo) that can be ruled out with different power levels and 95% confidence when there are 100 participants in the MK-8527 group and 50 participants in the placebo group. The underlying incidence of AE is assumed to be the same in the MK-8527 group as that in the placebo group. The calculations are based on an asymptotic method proposed by M&N method [Miettinen, O. and Nurminen, M. 1985]. No multiplicity adjustments were made.

Table 3 Difference in Incidence of AEs (MK-8527 Group Minus Placebo) That Can Be Ruled Out With 100 Participants in the MK-8527 Group and 50 Participants in the Placebo Group

Target Power	Difference a in Percentage Points That Can Be Ruled Out with Target Power Assuming the Underlying Incidence of the AE is				
	10%	20%	30%	40%	50%
80	20	23	24	24	23
85	21	24	25	26	25
90	23	26	27	28	27

aThe upper bound of the two-sided 95% confidence interval M&N method [Miettinen, O. and Nurminen, M. 1985] for the difference in AE incidences assuming the incidences are the same.

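### The planned AE confidence intervals make no use of the sex and region strata the trial randomises by, and no output serves the stated purposes of the race and gender-identity data

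*SAP*

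**What the plan says.** **Randomisation.** Protocol 6.3.1: "Participants will be assigned randomly in a 2:2:2:1 ratio" to 3 mg, 6 mg, 12 mg and placebo (about 100, 100, 100 and 50). Protocol 6.3.2 stratifies by sex and region. It first says "The effects of study interventions may differ between these subgroups of sex and region" and then that "sex and region are selected as the stratification factors to ensure that intervention groups will be well-balanced", so that effects are not confounded with them.

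**Analysis.** SAP 3.5.1 and 3.5.1.1 compare each dose with placebo, with Miettinen-Nurminen 95% intervals for eight overall AE rows. Neither section mentions the strata, nor does Protocol 9.5.1. Laboratory changes are summarised by treatment group. SAP 3.9 reads in full: "No subgroup analyses are prespecified in the protocol".

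**Stated purposes of other data.** Protocol 4.2.3 says "it is important to collect race and ethnicity data to ensure that there is not a differential effect based on these parameters". Protocol 4.2.4 says "Data will be collected in this study to assess clinical safety and toxicity in the transgender population".

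**The concern.** When randomisation is stratified, the arms are nearly balanced within strata. Variation between strata then contributes almost nothing to the true sampling error of the difference between arms. An unstratified interval still counts that variation. If the strata predict AE incidence, the interval is wider than it needs to be and covers more often than 95%. The protocol itself treats sex and region as factors that may matter, so the analysis should use them.

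Separately, a reader of Protocol 4.2.3 and 4.2.4 would expect some table or listing of safety by race and ethnicity, and for transgender participants. None is planned. At stake is modest precision on the primary safety contrasts, and consistency between what the protocol says the data are for and what will be reported.

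**Working it through.** **1. The plan's own figure.** SAP 3.8.1: "The power is based on the two-sample t-test assuming 100 participants in the MK-8527 group and 50 in the placebo group". For SD 20 and a 10-point difference:
- SE = 20 × √(1/100 + 1/50) = 3.464
- noncentrality = 10 / 3.464 = 2.887, with 148 degrees of freedom and two-sided critical value 1.976
- power from the noncentral t distribution = 81.8%, as in SAP Table 2

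The arm sizes are confirmed. The figure is for the overall population; the documents give none by stratum.

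**2. Unstratified AE interval.** Assume 40% incidence in both arms, within the 10% to 50% range of SAP Table 3. As a simple large-sample approximation, half-width = 1.96 × √(0.24/100 + 0.24/50) = 0.166, or about 17 points.

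**3. What stratifying removes.** With equal-sized strata and stratum rates p_k averaging p, the stratified-to-unstratified SE ratio is approximately √(1 − Var(p_k) / [p(1 − p)]). All stratum rates here are assumptions, since the documents give none:
- 40/40/40/40%: Var = 0; ratio 1.00.
- 20/40/40/60%: Var = (0.04 + 0 + 0 + 0.04)/4 = 0.020; ratio √(1 − 0.020/0.24) = 0.957.
- 20/30/50/60%: Var = (0.04 + 0.01 + 0.01 + 0.04)/4 = 0.025; ratio √(1 − 0.025/0.24) = 0.946. The half-width falls from 16.6 to 16.6 × 0.946 = 15.7 points. The unstratified interval then covers as if its multiplier were 1.96/0.946 = 2.07, which is about 96.2%.
- 10/30/50/70%: Var = (0.09 + 0.01 + 0.01 + 0.09)/4 = 0.050; ratio √(1 − 0.050/0.24) = 0.890.

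**4. Simulation of the actual method.** Miettinen-Nurminen intervals were computed both ways for 100 against 50 participants, with no true difference. Four strata were used, either equal, or 42/28/18/12 on active and 21/14/9/6 on placebo.
- Equal rates: width unchanged.
- The three unequal patterns above: about 3 to 4%, 4 to 5% and 9% narrower. The large-sample formula slightly overstates the gain in the widest case. Unstratified coverage was about 96 to 97%; stratified coverage was about 95%.
- Uniform rates of 1 to 2%: stratified intervals about 1% wider, with the same coverage as unstratified.

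**5. Sparse cells.** Protocol 4.1 targets at least 30% women, at least 30% men and at least 30% enrolled in Africa. If sex and region were independent and both at a 30% floor, the smallest placebo cell would hold 50 × 0.3 × 0.3 = 4.5 participants. That is small but not empty on average.

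**6. Precision of descriptive subgroup summaries.** A 30% subgroup, assumed to have the same share in each arm, gives 30 against 15:
- AE difference at 40% incidence: 1.96 × √(0.24/30 + 0.24/15) = 0.30, or ±30 points.
- 10-point lymphocyte difference, SD 20: power 33.9% by the method of step 1.
- Zero events among the 90 pooled MK-8527 participants: one-sided 95% upper bound 1 − 0.05^(1/90) = 3.3%.

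**The case against.** The case against has four parts.

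- **Purpose of the strata.** Sex and region are stratified for balance, and the randomisation delivers balance. A reader might infer that they are collected to check for differential safety. Protocol 6.3.2 does not say that. The case for stratifying the intervals does not need it: it rests on analysing by the factors used to randomise.
- **Need.** No passage requires stratified intervals, and an unstratified interval remains valid, if slightly conservative. With about 50 placebo participants over four strata and rows such as death that may have few events, stratification might look fragile. The first part stands, so this is an improvement and not the correction of an error. The fragility does not show in the simulation: the cost for rare events is about 1% in width.
- **Subgroup tables.** A reader might conclude that the trial cannot answer what the race and gender-identity data are for. The documents do not support that. The data are collected, and SAP Section 3 allows post hoc exploratory analyses if labelled as such. What is missing is prespecification. Protocol 4.2.4 promises description of safety in transgender participants, not a comparison. No minimum is set for any race group or for transgender participants, and precision will be poor. All of this stands, so the tables should be descriptive and this part is secondary.
- **PK.** A reader might also infer that PK by sex, region or race goes unexamined. SAP 3.5.4 refers to a separate population PK analysis plan whose covariates are not shown, so that cannot be established.

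**Conclusion.** The point holds as a minor improvement. The primary safety intervals ignore the randomisation strata. Using them costs almost nothing and narrows the intervals by about 0 to 9%, the larger gains requiring strong differences in AE incidence between strata. If sex and region do not predict AEs, nothing is gained and essentially nothing is lost. The size rests on assumed stratum rates, an overall incidence near 40%, and 100 against 50 participants.

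The secondary gap is one of reporting: for race, ethnicity and gender identity, the protocol states purposes that no planned output serves. For sex and region the gap is weaker, because the protocol says only that effects may differ by them. Summaries by these factors would be descriptive at best.

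**What to change.** **SAP 3.5.1.1.** State that the Miettinen-Nurminen 95% intervals for each dose against placebo are stratified by sex and region, with sample-size (Cochran-Mantel-Haenszel) weights. State in advance how strata are pooled if an arm has no participants in a cell. The cost is one option in existing programs.

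**SAP 3.9.** Add descriptive summaries, without tests, of the overall AE rows and of lymphocyte and CD4+ percent change by sex, region and race/ethnicity. Show them by dose and for pooled MK-8527 against placebo, and add a safety listing for transgender participants. Label them as imprecise. Alternatively, soften the purpose statements in Protocol 4.2.3 and 4.2.4. The cost is a few extra tables from data already collected.

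Both changes belong in a SAP amendment before the wider Sponsor unblinding after the last expected Follow-up Week 4 visit (Protocol 6.3.3), so that the choices are not made with results by arm in view.

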### **3.10 Compliance (Medication Adherence)**

Study intervention data for MK-8527 and placebo will be collected during the study. A day within the study will be considered an “On-Therapy” day if the participant takes the required number of pills from all containers provided for this study. A participant will have to take all 4 capsules per dose to be considered compliant.

For a participant who is followed for the entire study period, the “Planned Number of Days on Therapy” is the total number of days from randomization to the last scheduled day for treatment administration for that participant. For a participant who discontinued from the study permanently, the “Planned Number of Days on Therapy” is the total number of days from randomization to the date of the last dose of study medication.

For each participant, percent compliance will then be calculated using the following formula:

$$\text{Percent Compliance} = \frac{\text{Number of Days on Therapy}}{\text{Planned Number of Days on Therapy}} \times 100$$

Summary statistics will be provided on percent compliance by treatment group for the APaT population.

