7 DISCONTINUATION OF STUDY INTERVENTION AND PARTICIPANT WITHDRAWAL

7.1 Discontinuation of Study Intervention

Discontinuation of study intervention does not represent withdrawal from the study.

As certain data on clinical events beyond study intervention discontinuation may be important to the study, they must be collected through the participant's last scheduled follow-up, even if the participant has discontinued study intervention. Therefore, all participants who discontinue study intervention before completion of the protocol-specified treatment period (last dose at Week 20) will still continue to be monitored in the study and participate in the study visits and procedures as specified in Section 1.3 and Section 8.11.3 unless the participant has withdrawn from the study Section 7.2.

Participants may discontinue study intervention at any time for any reason or be discontinued from the study intervention at the discretion of the investigator should any untoward effect occur. In addition, a participant may be discontinued from study intervention by the investigator or the Sponsor if study intervention is inappropriate, the study plan is violated, or for administrative and/or other safety reasons.

A participant must be discontinued from study intervention, but continue to be monitored in the study for any of the following reasons:

- The participant or participant's legally acceptable representative requests to discontinue study intervention.
- The participant's treatment assignment is unblinded before Week 20.

Note: The need for the participant to be discontinued from study intervention due to unblinding will be determined collaboratively between the investigator and the Sponsor's Clinical Director.

- The participant has a medical condition or personal circumstance which, in the opinion of the investigator and/or Sponsor, placed the participant at unnecessary risk from continued administration of study intervention.

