If a participant discontinues study intervention before the final dose at Week 20, the EOT visit (Visit 11) should be performed in place of the next study visit. If a participant discontinues study intervention and also withdraws from the study before the final dose at Week 20, then only the EOT visit (Visit 11) should be performed in place of the next study visit. If a participant receives the final Week 20 dose of study intervention and then withdraws from the study, an “Early Withdrawal From Study” visit should be performed as the final study visit as outlined in Section 1.3.2 of the SoA.

8.11.3.1 Management of Participants with Specified Decreases in Total Lymphocyte Count or CD4+ T-cell Counts

Participants discontinued from study intervention (prior to the final dose at Week 20) due to confirmed decreases in total lymphocyte count or CD4+ T-cell count (Section 7.1 and [Table 3](#)) should undergo assessments for the EOT visit (Visit 11) as specified in the SoA in Section 1.3.1. To meet the protocol-defined discontinuation criteria, participants must have a confirmed total lymphocyte count or CD4+ T-cell count that indicates a specified decrease on 2 consecutive measurements 1 to 4 weeks apart ([Table 3](#)). Note: The time frame for confirmation of decreases in total lymphocyte count or CD4+ T-cell count may be extended in the setting of intercurrent illness, immunization, or study intervention dosing interruptions (due to missed study visits). Allow approximately 4 weeks following resolution of illness, immunization, or study intervention dosing interruptions before collecting the confirmation sample to allow for evaluation of a potential other causal effect. Consult with the Sponsor prior to discontinuation if the investigator believes there is an alternative explanation for the result (eg, COVID-19).

After discontinuation from study intervention, participants should continue to be followed in the study, by completing the follow-up visits as outlined in the SoA in Section 1.3.1.

Total lymphocyte counts and CD4+ T-cell counts will also be monitored during follow-up (after last dose at Week 20). If a participant has a confirmed decrease in total lymphocyte count or CD4+ T-cell count as per Section 7.1, [Table 3](#), after the last dose at Week 20, participants should continue to be followed in the study, by completing the follow-up visits as outlined in the SoA in Section 1.3.1.

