8.11.6 Follow-up Period

During the 8-week blinded follow-up period, all participants will complete 3 monthly follow-up visits: Follow-up Day 1, Follow-up Week 4, and Follow-up Week 8. PBMC Subset participants will have 1 additional follow-up visit at Follow-up Week 6.

The follow-up visits represent different study day/weeks for a participant that completes the final Week 20 dose and a participant that discontinues study intervention prior to Week 20, as outlined below.

A participant that completes the final Week 20 study intervention dose will return to the site for follow-up visits based on the following:

- **Visit 12/Follow-up Day 1 (all participants):** this visit should be completed ~24 hours after the Week 20 study intervention dose; PK samples must be collected 24 hours (± 6 hours) after the Week 20 dose.
- **Visit 13/Follow-up Week 4 (all participants):** this visit should be completed 24 weeks (± 7 days) from the Day 1 (Visit 2).
- **Visit 14/Follow-up Week 6 (PBMC Subset only):** this visit should be completed 26 weeks (± 2 days) from the Day 1 (Visit 2).

- **Visit 15/Follow-up Week 8 (all participants):** this visit should be completed 28 weeks (± 7 days) from the Day 1 (Visit 2).

A participant that discontinues study intervention prior to the Week 20 dose, will return to the site for follow-up visit based on the EOT (Visit 11) date:

- **Visit 12/Follow-up Day 1 (all participants):** this visit should be completed ~ 24 hours after the EOT visit (Visit 11).
- **Visit 13/Follow-up Week 4 (all participants):** this visit should be completed 4 weeks (± 7 days) from the EOT visit (Visit 11).
- **Visit 14/Follow-up Week 6 (PBMC Subset only):** this visit should be completed 6 weeks (± 2 days) from the EOT visit (Visit 11).
- **Visit 15/Follow-up Week 8 (all participants):** this visit should be completed 8 weeks (± 7 days) from the EOT visit (Visit 11).

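### SAP 3.10 scores six once-monthly doses with a day-count compliance formula: full adherence over a 141-day denominator scores 4.3%, or 100% on a reading that still gives 96.5% after five missed doses

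*SAP*

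**What the plan says.** SAP 3.10 builds the score from these parts:

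- **Numerator.** Something counts as an On-Therapy "day if the participant takes the required number of pills from all containers provided for this study". At dose level, "A participant will have to take all 4 capsules per dose to be considered compliant". Nothing is said about the days between monthly doses.
- **Denominator, participant followed for the whole study.** The planned number of days "is the total number of days from randomization to the last scheduled day for treatment administration for that participant".
- **Denominator, participant who has permanently left the study.** It "is the total number of days from randomization to the date of the last dose of study medication".
- **Use.** "Summary statistics will be provided on percent compliance by treatment group for the APaT population".

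The protocol adds the schedule and the handling of early stoppers. Protocol 8.1.8.1 (Table 4) sets six clinic doses with ideal days 1, 29, 57, 85, 113 and 141, and a dose outside its window is skipped. Protocol 7.1 states that "Discontinuation of study intervention does not represent withdrawal from the study". Under Protocol 8.11.3, for a participant who stops before Week 20, "the EOT visit (Visit 11) should be performed in place of the next study visit". Under Protocol 8.11.6 that participant "will return to the site for follow-up visit based on the EOT (Visit 11) date".

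**The concern.** A ratio of days on therapy to days planned suits daily dosing. Here the drug is taken on six days spread over about 20 weeks, so numerator and denominator are in different units unless the SAP says how the days between doses count. It does not. The committed table could then show a fully adherent group at about 4%, or show nearly everyone close to 100% however many doses were missed. Missed doses are foreseen: a dose outside its window is skipped (Protocol 8.1.8.1), and doses may be held for an adverse event (6.6), pending confirmation of a low lymphocyte or CD4+ count (7.1), or after a change in HIV risk (8.3.6). A compliance table should show these omissions. There is also a question of which denominator applies to participants who stop dosing and remain in follow-up, a group the protocol plans for.

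**Working it through.** The documents state no compliance figure, so there is none to reproduce.

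**Inputs.** Randomization is on Day 1 (Protocol 1.2). Ideal dosing days are 1, 29, 57, 85, 113 and 141 (Protocol Table 4; 20 × 7 + 1 = 141). The last scheduled day is taken as the ideal Day 141 and days are counted inclusively. The denominator is 141, with 6 dosing days and 141 − 6 = 135 non-dosing days.

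**Participant followed throughout, m doses missed.** On the literal reading only days with capsules taken count: (6 − m)/141. On the crediting reading non-dosing days also count: (141 − m)/141. The comparator is doses taken over doses planned: (6 − m)/6.

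| Doses missed | Literal | Crediting | Doses over 6 |
|---|---|---|---|
| 0 | 6/141 = 4.3% | 141/141 = 100% | 100% |
| 1 | 5/141 = 3.5% | 140/141 = 99.3% | 83.3% |
| 3 | 3/141 = 2.1% | 138/141 = 97.9% | 50.0% |
| 5 | 1/141 = 0.7% | 136/141 = 96.5% | 16.7% |

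On both day-count readings one missed dose moves the score by 1/141 = 0.71 points, and five move it by 5/141 = 3.5 points. With doses over 6, one missed dose moves it by 1/6 = 16.7 points. The 0.71 is not sensitive to the day convention: it is 1/140 = 0.71 if Day 1 is not counted, and 1/148 = 0.68 to 1/134 = 0.75 at the limits of the Week 20 window.

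**Participant who leaves the study.** The denominator ends at the last dose, so the cost of a miss changes. With the last dose on Day 57, all three doses taken gives 3/57 = 5.3% on the literal reading. Skipping Day 29 gives 2/57 = 3.5%, a drop of 1/57 = 1.75 points. With the last dose on Day 113 an earlier miss costs 1/113 = 0.88 points. Doses due after the last one taken do not enter the score at all.

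**Participant who stops intervention but stays in follow-up.** The score depends on which denominator is used:

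- Stop after Day 57: literal 3/141 = 2.1% or 3/57 = 5.3%; crediting 138/141 = 97.9% or 57/57 = 100%.
- Stop after Day 1: literal 1/141 = 0.7% or 1/1 = 100%; crediting 136/141 = 96.5% or 100%. If Day 1 is not counted, 1/1 becomes 1/0, which is undefined.

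The choice is not settled by the participant's own schedule. Take a participant outside the PBMC Subset whose EOT visit replaces Week 4 (Day 29). Follow-up Week 8 falls at Day 29 + 56 = Day 85, so Day 141 is never reached.

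**The case against.** Four counter-arguments deserve weight.

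1. **The authors may have had doses in mind.** The capsules-per-dose sentence points that way, and a convention in which each dose covers 28 days would be far more sensitive: a missed dose before Week 20 would cost 28/141 = 19.9 points. This stands in part. A reader might infer that every possible reading fails, and that goes too far. But the SAP states no coverage rule, so the table cannot be programmed on one.
2. **The 0.71 points is not universal.** A reader might apply it to everyone. It belongs to the 141-day denominator; for study leavers an earlier miss costs more. This stands.
3. **The scores do not always favor early leavers.** A reader might infer from 3/57 = 5.3% against 6/141 = 4.3% that leaving early always scores higher. That ordering exists only on the literal reading and can reverse: with a fifth dose on Day 120, the limit of the Week 16 window, a leaver scores 5/120 = 4.2%. On the crediting reading a leaver with no skipped dose scores 100%, the same as a completer.
4. **The second denominator may cover participants who stop intervention.** The protocol attaches permanence to stopping intervention (7.1), and the SAP rule refers to the last dose, so its wording about leaving the study may simply be loose. It cannot be said that this group is excluded. But Protocol 7.1 separates the two events, so coverage is ambiguous.

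Dosing is also witnessed in clinic, interruptions of one or more monthly doses require consultation with the sponsor (Protocol 6.4), and SAP 3.11 separately summarizes the amount of intervention received. This limits the practical effect but does not repair the table in SAP 3.10.

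**Conclusion.** The point holds, with severity minor. For participants with the 141-day denominator the formula is either mis-scaled or nearly blind to missed doses, and the SAP does not say which version is meant. The denominator for participants who stop intervention but remain in follow-up is ambiguous, and for a one-dose stopper on the literal reading the choice decides between 0.7% and 100%. These figures assume ideal dosing days and inclusive day counting.

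A reader might infer that the safety or PK conclusions are at risk. The documents do not support that: no endpoint, confidence interval, analysis population or stopping rule is defined by this percentage. The effect is confined to the descriptive compliance table.

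**What to change.** Replace the day-count ratio with full 4-capsule doses taken divided by doses planned, times 100, and state one denominator rule for all APaT participants. The sponsor chooses and labels it:

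- **All 6 planned doses**, labelled as adherence plus persistence; or
- **Dosing visits scheduled before discontinuation of intervention**, labelled as on-treatment compliance. The rule must say whether a dosing visit replaced by EOT counts; otherwise a one-dose stopper whose EOT replaces Week 4 scores 1/1 = 100% or 1/2 = 50%.

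As an illustration, a participant dosed on Days 1 and 57 only, who then stops, scores 2/6 = 33.3% under the first rule. Under the second the score is 2/3 = 66.7% if the three dosing visits up to Day 57 are those counted.

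With either rule, tabulate participants receiving 0 to 6 full doses by treatment group so that early stopping stays visible; this can serve as the SAP 3.11 summary. Show doses withheld under the protocol separately from other missed doses, so that following the protocol is not reported as non-compliance.

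The cost is a short SAP paragraph and some programming. Dosing time for each bottle is already reported on the eCRF (Protocol 6.1), which is enough for the ratio and the dose counts. Separating withheld doses also needs the reason for each. Protocol 6.4 and 6.6 already require written documentation of decisions on interruptions, but the sponsor should confirm that the reason is available in a form that can be tabulated.
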